1. BACKGROUND INFORMATION

1.1 Overview

Prostate cancer remains the most common solid organ malignancy in American men, with an estimated 238,590 new cases diagnosed in 2013 and an estimated 29,720 cancer-related deaths. (1) Prostate cancer screening through the use of prostate specific antigen (PSA) has dramatically increased the number of men diagnosed with prostate cancer annually, with most of the additional cases representing early stage disease. A large majority of men with early stage prostate cancer are receiving definitive treatment with radical prostatectomy (RP) or radiation therapy. Although some studies indicate that the early diagnosis and treatment of prostate cancer is associated with a decrease in prostate cancer specific mortality, (2) over 1,000 men had to be screened and 37 cancers detected to prevent a single death from prostate cancer. (3) This has led to controversy around over-treatment of many cases of indolent disease, resulting in needless morbidity and increased healthcare costs. These concerns regarding the over-diagnosis and over-treatment of early-stage prostate cancer have contributed to the recent recommendation by the US Preventive Task Force against PSA screening. (4)

Thus, many men diagnosed with prostate cancer in the PSA-screening era have a clinically indolent form of cancer that does not require immediate treatment and could instead be managed with active surveillance (AS) withholding treatment for curative intent if there are signs of progression. The uptake of this strategy, however, has been limited, with < 10 % of patients diagnosed with low-risk prostate cancer managed with AS according to a recent CaPSURETM registry survey. (5) A significant limitation to the use of AS is the uncertainty amongst clinicians regarding the accuracy of the current tools used to identify patients with low-risk disease (see (6) for review). A major limitation is the limited nature of biopsy sampling with several studies demonstrating GS upgrading in a substantial proportion of cases (20-60%), from GS 6 on biopsy to GS 7 and even GS 8 at RP. (7-9)

There is clearly a need for the development of new clinical tools that will allow for identification of biological characteristics that translate to a more accurate risk assessment for an individual patient's prostate cancer. A tool to reliably identify patients with clinically indolent prostate cancer would improve selection of patients with low risk disease who can be confidently managed by AS, have greater confidence and improved persistence on AS, and avoid the potential side effects and complications of unnecessary interventions. Alternatively, men found to be at increased risk of harboring aggressive disease could be directed towards immediate treatment with curative intent.

1.2 Oncotype DX Prostate Cancer Assay Development and Validation

Genomic Health has applied the development approach from its prior breast and colon cancer programs to develop a biopsy-based genomic assay to discriminate clinically indolent from

Protocol Number:	Revision Number:	Effective Date:	Page:
09-023	1.0		9 of 28

Gene identification study

A study was conducted to identify genes whose expression was associated with clinical recurrence, biochemical recurrence and death from prostate cancer. Of 2,641 subjects with clinical stage T1/T2 cancer who underwent RP at Cleveland Clinic from 1987 to 2004, a cohort sampling design was used to select 127 subjects with clinical recurrence (both local and metastatic) and 374 subjects without clinical recurrence after surgery.

Gene refinement study in prostate biopsy specimens

Protocol Number:	Revision Number:	Effective Date:	Page:
09-023	1.0		10 of 28

2. OBJECTIVES

[figure not shown]
The primary goal of this prospective study is to assess the rate of persistence on Active Surveillance (AS) in men who choose AS after receiving the Onco*type* DX Prostate Cancer GPS.

2.1 Primary Objective

2.1.1 To assess the rate of persistence on AS at 1 and 2 years after receiving the Onco*type* DX Prostate Cancer GPS

Protocol Number: 09-023	Revision Number: 1.0	Effective Date:	Page: 11 of 28

Protocol Number:	Revision Number:	Effective Date:	Page:
09-023	1.0	Effective Bute.	12 of 28

3. PHYSICIAN AND PATIENT ELIGIBILITY

Prior to enrolling any patients into the study, the principal investigator (PI) and all participating investigators at each site must complete the Site PI Initiation Form (see Appendix A). The site PI must acknowledge and sign the Protocol Signature Page (see Appendix B). These forms must be completed at the beginning of the study.

3.1 Pre-Study Physician Requirements

In order to review the implications of GPS on treatment decisions at all sites regardless of prior use of GPS, each participating physician will be required to take part in a review of the clinical development and validation data of the assay and a detailed review of the protocol. After participating physicians have completed their training sign-off and have IRB approval, the site may begin to enroll patients in this study.

3.2 Patient Management Plan

3.2.1 **Identification of Potentially Eligible Subjects**: Patients with very low, low, and low-intermediate risk prostate cancer (as defined in section 3.3.2 below) may be eligible for this study.

3.3 Inclusion Criteria

- 3.3.1 **Physicians:** Each of the criteria in the following section must be met in order for a physician to be considered eligible for registration:
 - 3.3.1.1 The physician is a urologist who makes primary treatment recommendations for patients with localized prostate cancer.
 - 3.3.1.2 The physician must practice at a facility or group practice that consults on at least 25 newly diagnosed prostate cancer patients per year who are very low, low, or intermediate risk as per NCCN guidelines (NCCN V3, 2012)
 - 3.3.1.3 The physician must practice in a group or setting that is experienced in offering AS. The Principal Investigator (PI) at each participating site must complete the Site Principal Investigator Initiation Form and Protocol signature page.
 - 3.3.1.4 The physician must participate in a review of Onco*type* DX Prostate Cancer Assay information and training materials, including assay development and validation data.
 - 3.3.1.5 The physician and participating site staff (including pathology if available) must participate in a review of this protocol including patient eligibility and protocol related training materials.
- 3.3.2 **Patients:** Patients eligible for this study will have been newly diagnosed with prostate cancer within the last 3 months, with no treatment decision made, and

Protocol Number: Revision Number: Effective Date: Page: 13 of 28

meet all Inclusion criteria and no Exclusion criteria. Eligible patients include those with:

- Clinical stage T1/T2
- $PSA \le 20 \text{ng/mL}$
- Biopsy GS ≤ 6 with any number of cores positive, or Biopsy GS 3+4 disease with ≤3 positive cores or ≤ 33% positive cores
- The patient must be > 50 years of age
- The patient must have a life expectancy of > 10 years, based on the Social Security Actuarial Life Table (see Appendix C).
- The patient must be able to give consent in English or Spanish

3.4 Exclusion Criteria

- 3.4.1 Physicians are excluded from participating if they are:
 - 3.4.1.1 Not responsible for the care of newly diagnosed prostate cancer patients who are candidates for AS
- 3.4.2 Patients are excluded from participating if they have/are any one of the following:
 - 3.4.2.1 Clinical stage T3a or above
 - 3.4.2.2 PSA > 20 ng/mL
 - 3.4.2.3 Biopsy GS 4+3 or ≥ 8
 - 3.4.2.4 Known metastatic prostate cancer (bone, lymph node etc.)
 - 3.4.2.5 Positive biopsy for prostate cancer > 3months ago
 - 3.4.2.6 Treatment decision has already been made
 - 3.4.2.7 Insufficient tumor in prostate biopsy tissue to perform the assay
 - 3.4.2.8 Treatment with androgen deprivation therapy (ADT) prior to prostate biopsy
 - 3.4.2.9 Diagnosis made by transurethral resection of prostate (TURP) shavings
 - 3.4.2.10 Any psychiatric or psychological condition, such as depression or anxiety, that would impede the patient's ability to give informed consent
 - 3.4.2.11 Contraindications to primary treatment according to physician's judgment

3.5 Target Enrollment

3.5.1 This study is targeted to enroll approximately 1200 patients, with no investigator contributing more than 50 patients.

Protocol Number:	Revision Number:	Effective Date:	Page:
09-023	1.0		14 of 28

3.6 Selection of Treatment Sites

This study will be conducted at approximately 25 large community based urology group practices and 5 academic sites in the United States. Site selection was based on:

- 3.6.1 Projected volumes of new prostate cancer cases per month who meet inclusion criteria
- 3.6.2 Experience with AS
- 3.6.3 The site's ability to conduct clinical studies in prostate cancer, including sufficient research personnel, experience, and infrastructure to obtain patient consent, manage questionnaires, and capture and transmit data to a central research coordinator
- 3.6.4 Expeditious contracting and IRB process

4. STUDY DESIGN

[figure not shown]
This is a multicenter observational study that evaluates eligible patients who will submit prostate cancer diagnostic biopsy tissues for Onco*type* DX Prostate Cancer Assay testing. At visit 1a, the patient consents to the trial, a pre-assay physician treatment recommendation will be made along with additional assessments defined in Section 6, Table 1, and the assay is ordered. At Visit 1b, the physician will review clinical data, the GPS report and discuss treatment options with the patient. At the following visit, Visit 1c, a shared physician-patient treatment decision (immediate treatment or AS) will be made.

[figure not shown]
Men selecting immediate treatment will be contacted one year from date of diagnosis biopsy to document treatment received and to assess treatment satisfaction and Quality of Life (QoL) metrics.

Men selecting AS as primary treatment will be followed to assess persistence on AS. There is no required or standardized AS protocol for this study and the intensity of surveillance will be at the discretion of the investigator. Patients will not be required, but may undergo a standard TRUS guided surveillance biopsy at one year. In this study, the Onco*type* DX Prostate Cancer Assay will be assessed on the diagnostic biopsy only and will not be assessed on subsequent biopsies. Patients will be queried at 12 and 24 months for assessment of decision satisfaction and Quality of Life metrics.

4.1 Duration of Study

Patients will be participating in the study from the time of consent until Visit 2 (Year 1) for those patients in the Immediate Treatment arm, and to Visit 4 (Year 2) for those patients in the AS arm. Patient questionnaires will be completed at those defined time points in the schedule of assessments for this study.

4.1.1 Early Termination/Withdrawal Procedures

The following patient situations will result in screen failures and these patients will not be included in any analysis:

- Patients who have signed a consent form, but for whom a sample was not sent to GHI
- Patients who have signed a consent form and had a sample submitted to GHI, but for whom no GPS was generated

Patients who sign a consent form and receive a valid GPS but do not choose either AS or immediate treatment at Visit 1c will be considered unevaluable.

Patients who enter the study on the AS arm, and who subsequently decide to undergo treatment, will be required to complete the End of Study (EOS) visit assessments. Those patients who are Lost to Follow Up (LTFU) will also have the EOS form completed. LTFU patients are defined as those that have had at least 3 contact attempts over a one-month period. Those patients who have been reported deceased or withdraw consent will also have the EOS form completed.

5. MATERIALS AND METHODS

The Onco*type* DX Prostate Cancer Assay is a commercially available diagnostic test that is designed to aid in a physician's treatment recommendation to a newly diagnosed prostate cancer patient. All the necessary elements for the study (requisition forms, sample

Protocol Number: Revision Number: Effective Date: Page: 16 of 28

preparation kits, shipping materials) will be provided by GHI and testing of all specimens will be performed at GHI at no charge to the patients or the clinical sites. Standard operating procedures will be followed at GHI when processing the specimens.

Patient Reported Outcomes (PROs) will be assessed at specified visits. These are questionnaire based, have been used in this disease state and include a pre and post GPS Decisional Conflict Scale, EPIC-CP; FACT-G and Decision Regret (12-15). These are validated, self-administered, recall instruments and will be available in English and Spanish.

6. STUDY CALENDAR AND ASSESSMENTS

Site Specific Assessments and Forms:

The following forms will be collected during the course of the study: Site Principal Investigator Initiation Form, Site Principal Investigator Protocol Signature Page, Enrollment Log and Non-Enrollment Log. Instructions for the completion and submission of these forms will be provided by GHI.

Assessments and Forms for each Enrolled Patient:

After a patient consents to participate in this study, the assessments and forms listed in the table below will be completed by the treating physician and submitted to GHI as instructed. The Onco*type* DX Prostate Cancer Assay is expected to report results within a 13-21 day turnaround time upon receipt of the tumor specimen at GHI's laboratory.

Completion of Forms for each Enrolled Patient:

- Data is expected to be entered into the EDC (Electronic Data Capture) system within 5 business days of the patient's visit.
- Queries are expected to be addressed and responded to within 5 days of issue.

Table 1: Study Schema

• Visits 1b and 1c may occur anytime within 4 months of consent (Visit 1a), as is suitable for the patient. Subsequent visits (Visits 2, 3 and 4) are based on the duration from the date of biopsy, not from Visit 1a.

Protocol Number: 09-023	Revision Number: 1.0	Effective Date:	Page: 17 of 28

Assessments	Visit 1a	1b	1c	2 M12	3 M18	4 M24	End of Study
							Juan
Eligibility Criteria	X						
Informed consent	Х						
GPS ordered	X						
Demographics	Х						
Clinical T-Stage and Physician Risk Assessment	Х						
Biopsy ¹	Х			X	X	Χ	X
PSA ¹	X			X	X	X	X
DRE ¹	Х			Х	X	X	Х
FACT-G	Х			X		X	
EPIC-CP	X			X		X	
Decisional Conflict Scale		X ²	χ^3				
Patient informed of GPS result		Χ					
Decisional aids provided	X ⁴	X ⁵					
Physician Treatment Recommendation	X ⁶						
Physician –Patient Shared Decision			X				
Physician perceived value of GPS			X				
Patient perceived value of GPS			X				
Persistence on Active Surveillance				Х	Х	Х	
Regret				Х		Х	
End of Study ⁷							X
Surgical Pathology ⁸				Х			

¹ completed at Visit 1a and any subsequent visit, if new results are available since prior visit

² administered **before** the patient sees the physician and obtains the GPS report.

³ administered at completion of the visit **after** discussing the treatment options with physician

⁴ disease specific decisional aid provided (i.e. AUA Prostate Cancer Brochure)

⁵ Onco*type* DX specific decisional aid provided (i.e. GPS Patient Brochure)

⁶ completed before ordering the Onco*type* DX prostate cancer assay

⁷completed if a patient moves to immediate treatment, withdraws consent, does not get a valid GPS score, dies or is LTFU.

⁸ completed if surgery was performed on a patient who chose immediate treatment

Protocol Number:	Revision Number:	Effective Date:	Page:
09-023	1.0		18 of 28

7. STATISTICAL ANALYSIS METHODS

7.1 Risk group and endpoint definitions

7.1.1 NCCN-based risk groups

Clinical risk groups, based on the NCCN criteria (modification of NCCN V.3, 2012), are defined as follows:

Very Low: Gleason Score \leq 6 and PSA \leq 10 ng/ml and Clinical T1c and \leq 2 positive cores and \leq 50% tumor in any core and PSA density \leq 0.15 ng/ml/g.

Low: Gleason Score ≤6 and PSA<10 ng/ml and Clinical T1c and not meeting criteria for Very Low

Low-Intermediate: Gleason Score 3+4 or PSA 10-20 ng/ml or Clinical T2 with either ≤ 3 positive cores or $\leq 33\%$ positive cores.

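### The NCCN-based analysis groups in 7.1.1 do not match the population eligible under 3.3.2: some eligible men meet no group, and PSA of exactly 10 can meet two

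*Combined protocol and SAP*

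**What the plan says.** **Eligibility.** Section 3.2.1 describes the candidates: "Patients with very low, low, and low-intermediate risk prostate cancer (as defined in section 3.3.2 below) may be eligible for this study". Section 3.3.2 defines no groups. It lists entry criteria: "Clinical stage T1/T2", PSA up to 20 ng/mL, and "Biopsy GS ≤ 6 with any number of cores positive, or Biopsy GS 3+4 disease with ≤3 positive cores" or at most 33% of cores positive. The core limit there is tied to Gleason 3+4; Gleason ≤6 carries none.

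**Analysis groups.** Section 7.1.1 opens with "Clinical risk groups, based on the NCCN criteria (modification of NCCN V.3, 2012), are defined as follows". Very Low requires Gleason ≤6, PSA ≤10, T1c, at most 2 positive cores, at most 50% tumor in any core and PSA density ≤0.15. Low is "Gleason Score ≤6 and PSA<10 ng/ml and Clinical T1c and not meeting criteria for Very Low". Low-Intermediate is "Gleason Score 3+4 or PSA 10-20 ng/ml or Clinical T2 with either ≤ 3 positive cores", with 33% of cores as the alternative limit.

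**Use.** Section 7.2 plans persistence on AS for each of the three groups. Section 7.3 takes the Low group among the first 300 men with valid GPS results for its main assessment of decision change, then treats all 300 as spanning the NCCN groups. Neither section has an unclassified category or a rule for a man who meets no group or two.

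**The concern.** A set of analysis groups should place every eligible man in exactly one group. These do not. The entry criteria admit Gleason ≤6, T2 men whatever their core count, while 7.1.1 bars T2 from Very Low and Low and, for men with PSA below 10, makes T2 count towards Low-Intermediate only when few cores are positive. Men on the wrong side of that limit are in the study and, if they choose AS, in the primary denominator, but in no row of the 7.2 breakdown.

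Followed literally, the group counts fall short of the AS cohort and Low-Intermediate omits the higher-volume Gleason ≤6, T2 men. Otherwise someone has to place them by a rule that 7.2 does not state. The double placement at PSA = 10 is the same defect in the other direction.

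**Working it through.** The plan gives no figure on this point to reproduce, so the check sets the entry criteria against the group definitions.

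**1. Two readings of the Low-Intermediate sentence.** Reading A: the core limit governs T2 only. Reading B: it governs all three branches (Gleason 3+4, PSA 10-20, T2). A man fails the limit when he has more than 3 **and** more than 33% positive cores.

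**2. Individual profiles, all within 3.3.2 on stage, PSA, Gleason score and cores.**

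| Profile | Very Low | Low | Low-Int., A | Low-Int., B |
|---|---|---|---|---|
| Gleason 6, T2, PSA 5, 6/12 cores (50%) | no | no | no | no |
| Gleason 6, T1c, PSA 15, 6/12 cores | no | no | yes | no |
| Gleason 6, T1c, PSA 10, 2/12 cores, other Very Low criteria met | yes | no | yes | yes |
| Gleason 6, T1a/T1b, PSA 5, any cores | no | no | no | no |

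Row 1 is the main gap and does not depend on the reading. Row 2 is a further gap under B only. Row 3 is the overlap: Very Low runs to PSA ≤10 and Low-Intermediate starts at 10. It is attainable, since density ≤0.15 at PSA 10 needs a gland of at least 10/0.15 = 66.7 g. Row 4 arises because 3.3.2 says T1 and 7.1.1 says T1c. The exclusion "Diagnosis made by transurethral resection of prostate (TURP) shavings" probably makes such men few.

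**3. Where the T2 gap starts.** At 4 positive cores on a 6-, 8- or 10-core biopsy (4/10 = 40%). On 12 cores, at 4 if 33% is strict (4/12 = 33.3%), or at 5 if rounded to a whole percent (5/12 = 41.7%). On 14 cores, at 5 (4/14 = 28.6%; 5/14 = 35.7%).

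**4. Enumeration.** Grid: Gleason 6 or 3+4; PSA 5, 9.9, 10.1, 15, 20; T1c or T2; 1 to 12 positive of 12 cores; 33% strict. PSA = 10 is left to row 3 above. These are profiles, not men.

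- Eligible: Gleason 6, 5 × 2 × 12 = 120; Gleason 3+4, 5 × 2 × 3 = 30; total 150.
- No group, reading A: 2 PSA values × T2 × 9 core counts (4-12) = 18.
- No group, reading B: 18 + (3 PSA values × 2 stages × 9) = 18 + 54 = 72.
- No group if the core limit is attached to Gleason 3+4 only: 0.
- With 33% rounded (160 eligible): 16, 64 and 0.

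Moving the core limit thus closes the gap for T1c and T2 men. It does not remove the overlap at PSA = 10 or place T1a/T1b men.

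**5. Possible size; every input here is assumed.** Each 1% of the 300 AS men is 3 men; a share of 2% to 15% would be 6 to 45. If *U* men are left out of a Low-Intermediate group of *n*, and their persistence differs by *d* points, the group estimate with and without them differs by U/(U + n) × d:

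- U = 3, n = 100, d = 10: 3/103 × 10 = 0.3 points
- U = 15, n = 80, d = 10 to 20: 15/95 × d = 1.6 to 3.2 points
- U = 30, n = 60, d = 20 (extreme): 30/90 × 20 = 6.7 points

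For scale, the exact 95% CI for 50/60 (83.3%) is 71.5% to 91.7%, that is 11.8 points below and 8.4 above the estimate. For 83/100 it is 74.2% to 89.8%. Even the extreme case stays inside the interval.

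**The case against.** **The intended placement is evident.** Sections 3.2.1 and 7.3 write as if every enrolled man has a group. An eligible T2 man cannot be Very Low or Low, so he can only be Low-Intermediate. That is a sensible inference, but it overrides a core limit that 7.1.1 states expressly. It supports the proposed wording; it does not replace it.

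**The limit may be deliberate.** Section 7.1.1 calls itself a modification of an NCCN version, which was not consulted here, so intent cannot be judged. This stands, and the fix allows for it. A deliberate narrowing would still leave eligible men unreported in 7.2.

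**The estimate is not wrong.** Persistence in Low-Intermediate as 7.1.1 defines it is estimated correctly without these men; the shifts above only measure the distance to another definition. This stands too: no bias is shown.

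**Choosing after outcomes.** A reader might infer that men would be placed once their persistence is known. The documents do not support that. Section 7.3 needs the grouping for the first 300 men, and 7.5 repeats that analysis on all enrolled men when all have completed Visit 1c, before the planned persistence analysis at Visit 2. This does not guarantee a rule for the T2 men, but it weakens the scenario.

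**Limits of the text.** The PSA overlap turns on ≤10 for Very Low as it reads in the copy reviewed. The text of 7.4 was not available, so the claim is only that 7.1.1 to 7.3 give no rule.

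**Conclusion.** The point holds as a mismatch between two sections. The groups in 7.1.1 are neither exhaustive over the men eligible under 3.3.2 nor, at PSA = 10, mutually exclusive. The T2 gap follows from the text under either reading; the wider PSA 10-20 gap depends on reading B. The documents do not say how many men are concerned, and the effect on the 7.2 subgroup estimates, which are descriptive with no test attached, may be negligible. The correction is worth making because the breakdown concerns the primary endpoint and costs almost nothing to repair.

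Three stronger conclusions might be inferred and are not supported:

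- **That the primary result or sample size is compromised.** Overall persistence and the figure of 300 do not use the groups.
- **That the 7.3 change rates are distorted.** T2 men are outside Low in any case, and the overall rate is taken over all 300. T1a/T1b men would matter to the Low subset only if they were meant to count as Low.
- **That the biological groups in 7.1.2 have the same gap.** Their probability bands cover every rounded value, and the documents do not say whether a man without a 7.1.1 group can be given that probability.

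**What to change.** Before the first grouped analysis, which is the 7.3 analysis of the first 300 men, reconcile 7.1.1 with 3.3.2 for analysis classification only, leaving eligibility and patient management as they are:

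1. Attach the core limit to Gleason 3+4 only, as 3.3.2 does, so that every eligible T2 man with Gleason ≤6 is counted in Low-Intermediate, and PSA 10-20 counts without a core limit.
2. Assign PSA = 10 to one group only.
3. State where any non-T1c T1 men are counted.

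If the narrower core limit is deliberate, keep it, say which branches it governs, and add an unclassified row to the 7.2 breakdown so that the counts sum to the AS cohort. Items 2 and 3 still apply.

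The cost is one or two lines of wording or one table row. No new data are needed: the Section 6 schedule already collects "Clinical T-Stage and Physician Risk Assessment", biopsy and PSA at Visit 1a.
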